#### 8.8.4. Output

Output will include the following:

A PDF report including an executive summary and the following tables and figures.

- Table 1. Mock table shell: Study attrition of individuals with a record of immunoglobulin prescription among the general study population, presented by data source (*objective 1*).

	CDW Bordeaux	IQVIA DA Germany	CPRD GOLD
Qualifying initial records			
Cohort start date between 1/1/2017 and 31/12/2024			

- Table 2. Mock table shell: Study attrition of individuals initiating immunoglobulin treatment among the general study population, presented by data source (*objectives 3–4*).

	CDW Bordeaux	IQVIA DA Germany	CPRD GOLD
Qualifying initial records			
Cohort start date between 1/1/2017 and 31/12/2024			
Immunoglobulin prescription			
Prior history requirement*	NA		
No immunoglobulin record in 180 days prior to study inclusion*	NA		
Potential 180 days of follow-up			

\* = not required for hospital data sources

- Table 3. Mock table shell: Number of immunoglobulin prescriptions, treatment duration, and dose (initial, cumulative) of immunoglobulin use during the study period, per immunoglobulin brand, per data source.

Variable	Format	CDW Bordeaux	IQVIA DA Germany	CPRD GOLD
Number of subjects	N			
Number of records	N			
Immunoglobulin brand A				
Initial dose	Median [q25 – q75]			
	Mean			
	Min-max			
Cumulative dose	Median [q25 – q75]			
	Mean			
	Min-max			
Number of exposures	Median [q25 – q75]			
	Mean			
	Min-max			
Days exposed	Median [q25 – q75]			
	Mean			
	Min-max			
Immunoglobulin brand B/C/D, etc.				
Initial dose	Median [q25 – q75]			
	Mean			
	Min-max			
Cumulative dose	Median [q25 – q75]			

Variable	Format	CDW Bordeaux	IQVIA DA Germany	CPRD GOLD
	Mean			
	Min-max			
Number of exposures	Median [q25 – q75]			
	Mean			
	Min-max			
Days exposed	Median [q25 – q75]			
	Mean			
	Min-max			

- Table 4. Mock table shell: Demographic characteristics of individuals initiating immunoglobulin therapy at index date, per immunoglobulin brand, per data source.

Variable	Format	CDW Bordeaux	IQVIA DA Germany	CPRD GOLD
Immunoglobulin brand A				
Number of subjects	N			
Number of records	N			
Cohort start date*	Median			
Cohort end date*	Median			
Prior observation	Median [q25 – q75]			
Future observation	Median [q25 – q75]			
Age(years)	Median [q25 – q75]			
	Min-max			
Age group (years)				
• 1 to 18	N (%)			

Variable	Format	CDW Bordeaux	IQVIA DA Germany	CPRD GOLD
• 19 to 65	N (%)			
• >65	N (%)			
Sex				
• Male	N (%)			
• Female	N (%)			
Immunoglobulin brand B/C/D, etc.				
Number of subjects	N			
Number of records	N			
Cohort start date	Median			
Cohort end date	Median			
Prior observation	Median [q25 – q75]			
Future observation	Median [q25 – q75]			
Age (years)	Median [q25 – q75]			
	Min-max			
Age group (years)				
• 1 to 18	N (%)			
• 19 to 65	N (%)			
• >65	N (%)			
Sex				
• Male	N (%)			
• Female	N (%)			

\* = Interquartile ranges for cohort start and end date can be found in the Shiny app.

- Table 5. Mock table shell: Indications of use of individuals initiating immunoglobulin therapy during the study period, per immunoglobulin brand, per data source.

Indication of use	Any time prior to 7 days after index date [-inf, +7]			30 days prior to 7 days after the index date [-30, +7]			7 days prior to 7 days after the index date [-30, +7]		
	CDW Bordeaux	IQVIA DA Germany	CPRD GOLD	CDW Bordeaux	IQVIA DA Germany	CPRD GOLD	CDW Bordeaux	IQVIA DA Germany	CPRD GOLD
	n (%)	n (%)	n (%)	n (%)	n (%)	n (%)	n (%)	n (%)	n (%)
Immunoglobulin brand A									
Primary immunodeficiency syndrome									
Secondary immunodeficiencies									
Neurology									
Haematology									
Infectious diseases									
Solid organ transplantation									
Internal medicine									
Dermatology									
Hepatology									
Other indications*									
Immunoglobulin brand B/C/D, etc.									
Primary immunodeficiency syndrome									
Secondary immunodeficiencies									

Indication of use	Any time prior to 7 days after index date [-inf, +7]			30 days prior to 7 days after the index date [-30, +7]			7 days prior to 7 days after the index date [-30, +7]		
	CDW Bordeaux	IQVIA DA Germany	CPRD GOLD	CDW Bordeaux	IQVIA DA Germany	CPRD GOLD	CDW Bordeaux	IQVIA DA Germany	CPRD GOLD
	n (%)	n (%)	n (%)	n (%)	n (%)	n (%)	n (%)	n (%)	n (%)
Neurology									
Haematology									
Infectious diseases									
Solid organ transplantation									
Internal medicine									
Dermatology									
Hepatology									
Other indications*									

\* = Frequencies of 'Other indications' will be provided overall and separately for each indication, where available.

- Table 6. Mock table shell: Top 10 recorded conditions in individuals initiating immunoglobulin therapy, prior to the index date, per immunoglobulin brand, categorised by data source.

Any time prior to the index date [-inf, 0]						One year prior to the index date [-365, 0]						One month prior to the index date [-30, 0]					
CDW Bordeaux		IQVIA DA Germany		CPRD GOLD		CDW Bordeaux		IQVIA DA Germany		CPRD GOLD		CDW Bordeaux		IQVIA DA Germany		CPRD GOLD	
Condition	n (%)	Condition	n (%)	Condition	n (%)	Condition	n (%)	Condition	n (%)	Condition	n (%)	Condition	n (%)	Condition	n (%)	Condition	n (%)
Immunoglobulin brand A																	
Condition 1																	
Condition 2																	
Condition 3																	
Condition 4																	
Condition 5																	
Condition 6																	
Condition 7																	
Condition 8																	
Condition 9																	
Condition 10																	
Immunoglobulin brand B/C/D, etc.																	
Condition 1																	
Condition 2																	
Condition 3																	
Condition 4																	
Condition 5																	

[figure not shown]
Any time prior to the index date [-inf, 0]						One year prior to the index date [-365, 0]						One month prior to the index date [-30, 0]					
CDW Bordeaux		IQVIA DA Germany		CPRD GOLD		CDW Bordeaux		IQVIA DA Germany		CPRD GOLD		CDW Bordeaux		IQVIA DA Germany		CPRD GOLD	
Condition	n (%)	Condition	n (%)	Condition	n (%)	Condition	n (%)	Condition	n (%)	Condition	n (%)	Condition	n (%)	Condition	n (%)	Condition	n (%)
Condition 6																	
Condition 7																	
Condition 8																	
Condition 9																	
Condition 10																	

- Table 7. Mock table shell: Common infections among individuals who initiated immunoglobulin therapy during the study period, provided per immunoglobulin brand, per data source.

Indication of use	CDW Bordeaux		IQVIA DA Germany		CPRD GOLD	
	[0, +30]	[0, +365]	[0, +30]	[0, +365]	[0, +30]	[0, +365]
	n (%)	n (%)	n (%)	n (%)	n (%)	n (%)
Immunoglobulin brand A						
Pre-specified infection A						
Pre-specified infection B						
Pre-specified infection C/D/E, etc.						
Immunoglobulin brand B/C/D, etc.						
Pre-specified infection A						
Pre-specified infection B						
Pre-specified infection C/D/E, etc.						

- Table 8. Mock table shell: The frequency of antibiotics prescribed among individuals initiating immunoglobulin therapy during the study period, provided per immunoglobulin brand, per data source.

Indication of use	CDW Bordeaux		IQVIA DA Germany		CPRD GOLD	
	[0, +30]	[0, +365]	[0, +30]	[0, +365]	[0, +30]	[0, +365]
	n (%)	n (%)	n (%)	n (%)	n (%)	n (%)
Immunoglobulin brand A						
Pre-specified antibiotic A						
Pre-specified antibiotic B						
Pre-specified antibiotic C/D/E, etc.						
Immunoglobulin brand B/C/D, etc.						
Pre-specified antibiotic A						
Pre-specified antibiotic B						
Pre-specified antibiotic C/D/E, etc.						

- Mock figure: Annual prevalence of immunoglobulin use, overall and stratified by ingredient, per data source.

In addition to the mock figure above, the following figures will also be provided:

- 'Annual prevalence of immunoglobulin use, stratified by ingredient and route of administration, per data source'
- Annual prevalence of immunoglobulin use, stratified by ingredient and sex, per data source'
- 'Annual prevalence of immunoglobulin use, stratified by ingredient and age group, per data source'
- 'Quarterly prevalence of immunoglobulin brands, per data source'

An interactive dashboard will be generated by incorporating all the results (tables and figures) included in the PDF report mentioned above.

## 8.9. Evidence synthesis

Results from analyses described in [Section 8.8](#) will be presented separately for each data source. No meta-analysis of results will be conducted.

## 9. STRENGTHS AND LIMITATIONS

### Strengths

This study leverages several real-world data sources from three European countries, including France, Germany, and the United Kingdom, covering primary care and hospital care data sources. These data sources enable a comprehensive assessment of immunoglobulin use and patient characteristics across varied healthcare settings. Use of the OMOP CDM ensures standardised data structuring, harmonised variables, and consistent cohort definitions across sources. This facilitates reproducible analyses and enables robust characterisation of demographic and clinical profiles of individuals initiating immunoglobulin treatment and trends of immunoglobulin use during the study period.

### Limitations

The study will be informed by routinely collected healthcare data, which introduces several important considerations that may influence the interpretation of the findings.

The study will include data from three European countries. As such, the results reflect only the populations captured within these data sources and may not be generalisable to other countries or healthcare systems.

Electronic health records are primarily designed for clinical purposes rather than research, and as such, may contain incomplete, inconsistent, or variably recorded information. Therefore, the documentation of comorbidities, necessary for patient-level characterisation, may vary across data sources. The actual clinical indication for prescribing immunoglobulins is not directly recorded in the data sources. Instead, proxy measures based on diagnosis codes around the time of the first treatment during the study period are used. Consequently, the estimation of potential indications may be incomplete or imprecise as this might not be recorded in all patients. To minimise incompleteness, different time windows around the immunoglobulin prescription date will be applied to assess the indication of use.

Additionally, a recorded prescription does not guarantee that the medication was dispensed or consumed, therefore assumptions of actual use have been made. Furthermore, the type of health care setting may affect the prevalence of prescriptions of specific immunoglobulin types, e.g., intravenous immunoglobulins are predominantly administered in a hospital setting and not in primary care. The general study population which will be included to estimate the prevalence of immunoglobulin use may also be affected by the type of health care setting and the definition of the observation period by each data source. Primary care data sources generally encompass a broader cohort of individuals, observed from registration until deregistration (CPRD GOLD) or from first to last recorded event (IQVIA DA Germany), while the hospital data source (CDW Bordeaux) comprises individuals requiring inpatient care which are observed from their first to last visit.

To ensure comprehensive characterisation of all incident individuals, a minimum of 180 days of prior data availability is required for primary care data sources. This criterion may reduce the study size and will not be applied for hospital-based settings, where patients typically seek care for acute or specialised conditions and might, as a result, not have a long duration of longitudinal registration, as would be expected in a primary care setting data sources. Consequently, for CDW Bordeaux, it is uncertain whether included individuals are true incident users. Moreover, only a subset of included patients from hospital-based settings may contribute to time windows prior to the index date. The prior observation requirement may also imply selection bias favouring chronic indications, i.e., data in some pathological conditions may be limited or absent.

Of note, certain brands of interest cannot be assessed in the current study due to limitations, such as market authorisation occurring after the study period or the unavailability of an RxNorm code for those specific brands.

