### 8.8.3. Statistical model specification and assumptions of the analytical approach considered

#### Objective 1

Trends of immunoglobulin use during the study period will be assessed based on OMOP CDM mapped data using the *IncidencePrevalence* R package (<https://github.com/darwin-eu/IncidencePrevalence>), developed by DARWIN EU®.

The prevalence of individuals with a recorded immunoglobulin prescription (expressed as the proportion of individuals with any immunoglobulin prescription in the general study population) will be presented by immunoglobulin ingredient, route of administration, and stratified by sex and age.

Prevalence will be calculated as overall and annual, which summarises the total number of individuals with recorded immunoglobulin use during a given period divided by the population at risk of receiving immunoglobulins during that period. Therefore, period prevalence will give the proportion of individuals exposed at any time during a specified interval. Binomial 95% confidence intervals will be calculated.

#### Objective 2

Trends of immunoglobulin use during the study period will be assessed based on OMOP CDM mapped data using the *IncidencePrevalence* R package (<https://github.com/darwin-eu/IncidencePrevalence>), developed by DARWIN EU®.

The quarterly prevalence of individuals with prescriptions for prespecified immunoglobulin brands will be estimated (expressed as the proportion of individuals prescribed each specific immunoglobulin brand among prevalent immunoglobulin users).

Prevalence will be calculated as quarterly period prevalence, which summarises the total number of individuals with recorded immunoglobulin brand prescription during a quarter divided by the population of prevalent immunoglobulin users during that period. Therefore, period prevalence will give the proportion of individuals exposed to a specific brand at any time during the specified interval. Binomial 95% confidence intervals will be calculated.

An illustration of the calculation of period prevalence is shown below in **Figure 3**. Between time  $t+2$  and  $t+3$ , two of the five study participants receive immunoglobulin treatment, giving a prevalence of 40%. Meanwhile, for the period  $t$  to  $t+1$  all five also had some observation time during the year with one of the five study participants having a recorded immunoglobulin prescription, giving a prevalence of 20%.

[figure not shown]

Figure 3. Prevalence example.

### Objective 3

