## ANNEX II. Fitness for use assessment

### Data source justification for inclusion and key characteristics

#### **France: Clinical Data Warehouse of Bordeaux University Hospital (CDW Bordeaux)**

CDW Bordeaux will be included in this study because it is a hospital data source that provides relevant information on the use of immunoglobulins in the general population.

Based on a preliminary feasibility assessment, the expected number of person counts for immunoglobulin use in CDW Bordeaux will be 10,900.

Moreover, data availability and follow-up in CDW Bordeaux is sufficient, as data availability starts in 2005, and the date of most recent data extraction is 09/2025, which aligns with the study period. The median follow-up of the first observation period is 247 days.

There are no study specific limitations present in CDW Bordeaux.

Lastly, IRB approval for CDW Bordeaux is estimated to take 1 to 2 weeks, which makes the execution of this study feasible within the current study timelines.

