#### **Germany: IQVIA Disease Analyzer Germany (IQVIA DA Germany)**

IQVIA DA Germany will be included in this study because it is a primary care data source that provides relevant information on the use of immunoglobulins in the general population.

Based on a preliminary feasibility assessment, the expected number of person counts for immunoglobulin use in IQVIA DA Germany will be 47,500.

Moreover, data availability and follow-up in IQVIA DA Germany is sufficient, as data availability starts in 1989, and the date of most recent data extraction 12/2024, which aligns with the study period. The median follow-up of the first observation period is 116 days.

There are no study specific limitations present in IQVIA DA Germany.

Lastly, IQVIA DA Germany requires no IRB approval, which makes the execution of this study feasible within the current study timelines.

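### Near the end of the data, annual prevalence in IQVIA DA Germany (mainly 2024), and to a lesser extent CDW Bordeaux, is biased upward because observation stops at the last recorded contact

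*Protocol*

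**What the plan says.** Under Limitations, Protocol Section 9 gives the observation rule for each source. In the two primary care sources people are "observed from registration until deregistration (CPRD GOLD) or from first to last recorded event (IQVIA DA Germany"). The hospital source "comprises individuals requiring inpatient care which are observed from their first to last visit".

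Section 8.8.3, Objective 1, defines the measure, both for each year and for the whole study period. The numerator counts people with a record of use in the interval, and that count is "divided by the population at risk of receiving immunoglobulins during that period". The worked example for Figure 3, printed under Objective 2 but illustrating period prevalence generally, shows who enters the denominator: "all five also had some observation time during the year". So any observation time in the year is enough.

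The study period ends on 31/12/2024. Annex II gives the data ends. For IQVIA DA Germany it is "the date of most recent data extraction 12/2024, which aligns with the study period". For CDW Bordeaux, "the date of most recent data extraction is 09/2025".

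Section 9 also notes in general terms that the prevalence population may depend on how each source defines its observation period. Annex II records no study-specific limitation for either source. Table S1 marks the Objective 1 population as not applicable for the fitness assessment, and the ENCePP checklist marks sensitivity analyses as not applicable.

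**The concern.** When observation ends at the last recorded contact, membership of a year's denominator depends on what happens after that year. In 2019 a patient with no contact that year, but with contacts before and after, is counted. In 2024 the same patient is counted only if a later contact falls before the data end. For Germany that window has length zero. For Bordeaux it is about nine months. CPRD GOLD uses registration dates and does not have the problem.

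The numerator loses nobody in the same way, because an immunoglobulin record in the year is itself a contact in the year. The early years have no mirror image of similar size: look-back reaches 1989 in Germany and 2005 in Bordeaux, 28 and 12 years before 2017. The distortion is therefore one-sided and sits at the end of the series.

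This matters because Objective 1 exists to show annual trends, Section 8.8.4 plots them by ingredient, route, sex and age, and the rationale is that demand rises every year. An artefact in the expected direction, in two of three sources, could be read as confirmation or as a real difference between countries. The binomial intervals do not reflect it.

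**Working it through.** **The plan's own figure.** The Figure 3 text gives 2/5 = 40% and 1/5 = 20%. Both reproduce only if all five people with some observation time in the period are counted, which confirms the denominator rule.

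**Inputs from the protocol.** Observation rules (Section 9); denominator (Section 8.8.3); data ends 12/2024 and 09/2025, taken as E = 2025.0 and E = 2025.75; median follow-up of the first observation period 116 days (Germany) and 247 days (Bordeaux), both from Annex II.

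**Assumed, because the protocol gives no figure.** Contact rate λ per person-year and the length of time a person truly stays with the practice or hospital.

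**Step 1, closed form.** Take a person already known to the source on 1 January of year y and still truly present. That person is in the denominator only if another contact falls before E, with probability p(y) = 1 − exp(−λ(E − y)). With constant use, the spurious ratio of 2024 to 2017 within this group is p(2017)/p(2024).

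| λ per year | Germany | Bordeaux |
|---|---|---|
| 4 | 1.02 | 1.00 |
| 2 | 1.16 | 1.03 |
| 1 | 1.58 | 1.21 |
| 0.5 | 2.50 | 1.69 |

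Example for Germany, λ = 1: (1 − exp(−8))/(1 − exp(−1)) = 0.9997/0.632 = 1.58. New entrants are always counted in their year of entry, so the effect on the whole denominator is smaller than these values.

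**Step 2, simulation of the whole denominator.** True use constant; exponential stay with mean 2 to 10 years; Poisson contacts at the same rate for everyone; 2024 relative to the mean of 2017–2019.

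| λ per year | Germany 2024 | Bordeaux 2024 |
|---|---|---|
| 4 | at most 1.02 | 1.00 |
| 2 | 1.05–1.12 | 1.01–1.02 |
| 1 | 1.15–1.42 | 1.04–1.15 |
| 0.5 | not used in the range quoted | 1.11–1.43 |

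Germany 2023 is about 1.00–1.01 at two contacts a year and at most 1.12 at one.

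**Step 3, unequal contact rates.** If rates differ between people (gamma-distributed; mean stay 5 or 10 years; 0% or 40% attending only once; reference year 2019), the ratios are higher at the same mean rate. Germany 2024 is 1.10–1.15 at a mean of 4, 1.17–1.27 at 2, and 1.28–1.49 at 1. Bordeaux 2024 is 1.04–1.07, 1.08–1.13 and 1.13–1.23. Across all 48 scenarios, with mean rates from 0.3 to 6 a year, no 2023 or 2024 ratio pointed downward.

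**Step 4, comparison with the stated follow-up.** The upper German value in Step 2 (1.42: one contact a year, ten-year stay) implies a median follow-up of about 1,590 days, far above 116. The upper Bordeaux value (1.43: 0.5 a year, ten-year stay) implies about 1,300 days against 247. Long stays fit the stated medians only if many patients attend once. In Step 3, the German scenarios with a median of roughly 40 to 230 days give 2024 ratios of about 1.04 to 1.49, the top value at 0.5 contacts a year. In Step 2 the German scenario nearest 116 days (one contact a year, two-year stay, median 186 days) gives 1.15. The stated median does not settle the size.

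**The case against.** Four points on the other side carry weight.

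- **The size may be trivial.** With four contacts a year at a common rate, Germany 2024 is off by at most 2%. A reader might infer that the plan will show a visible rise in 2023–2024. The protocol does not support that: it gives no contact frequency, and 2023 moves little unless contacts are sparse.
- **Bordeaux is partly protected.** Its nine further months refill much of the 2024 denominator. Treating it like Germany needs contacts rarer than one a year. No passage states such a rate, and Annex I says the source includes outpatient specialist care. Section 9 does say hospital patients often come for acute or specialised conditions, so sparse contacts cannot be ruled out.
- **The count need not fall.** The denominator shrinks relative to the people truly present; the raw number can still grow if the database grows.
- **Section 9 already warns about observation periods.** It does so in general terms, as a matter of differing settings and source definitions. It does not say that coverage changes over calendar time within a source, which is what affects a trend. Reporting each source separately does not address this either.

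It is also tempting to conclude that the Objective 1 denominator must be replaced. That does not follow. A denominator of attenders answers a different question from prevalence in the general population, and it moves with any change in attendance.

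**Conclusion.** The direction of the bias follows from the protocol's own definitions: prevalence in the last year is biased upward in IQVIA DA Germany, and less so in CDW Bordeaux, even if use is constant. Under assumed common rates of 1 to 4 contacts a year, 2024 is inflated by about 1% to 40% in Germany and about 0% to 15% in Bordeaux, and by more in Bordeaux if contacts are rarer than one a year. Unequal contact rates raise these figures somewhat. The year 2023 is affected mainly when contacts are sparse. All sizes rest on assumed contact rates and lengths of stay; only the direction rests on the documents alone.

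A rule that the final-year inflation equals 1 divided by the share of a mid-period denominator with a contact in that year works for Germany, where the last study year is also the last data year. It should not be carried over to Bordeaux: at one contact a year and a ten-year stay it gives 1.43 against a simulated 1.15, and at two a year 1.13 against 1.02.

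**What to change.** 1. Keep the planned denominator for the Objective 1 prevalence level.
2. For IQVIA DA Germany and CDW Bordeaux, add a sensitivity trend whose denominator is people with at least one recorded contact or visit in that calendar year.
3. Report the annual denominator counts for each source.
4. State in Section 9 and on the trend figures that the last year (Germany 2024 above all, with Germany 2023 and Bordeaux 2024 flagged as possibly affected) is not to be interpreted as a rise in use unless the sensitivity trend shows it too.

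Cost: one extra denominator cohort in the study code, an added series in the figures and a short passage of text. The sensitivity estimates are per person attending, so they lie higher than the main estimates and also respond to changes in attendance. They serve to check the trend and do not replace the main result.
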